3.3	
Sample size Describe calculation of sample size or reference to sample size calculation in study protocol
	
Primary outcome: Based on the randomised clinical study of myopic children using DIMS spectacle lenses (Lam et al. 2020) standard error of mean was 0.02 mm and $n = 79$ in the DIMS group, hence the standard deviation (Smith et al. 2010) was calculated to be $SE = \frac{SD}{\sqrt{n}}$ given a SD of 0.178 mm. Based on the CONTROL-study (Jakobsen & Møller 2021) the SD of the treatment effect after 18 months was 0.18 mm in the OKL group. A sample size calculation for a non-inferiority study between the two groups given a significance level of 0.025 (one-sided test) and a power of 80% with a mean difference between treatment groups of 0.13 mm and a SD of 0.18 mm the sample size for each group should be 32 children. With an expected drop out of 30% a total of 42 children will be needed in each group.
 
A difference of 0.13 mm was chosen with reference to the correlation between change in cycloplegic spherical equivalent refractive error and axial length equivalent to 0.25D for female subjects aged 6 to 12 years in a Danish population (Jakobsen, Gehr & Møller 2020). 0.25D is the minimum measurement increment of refraction itself. Thus, to conclude non-inferiority, the difference between the two treatments (DIMS and OKL) need to be equal to, or less than, 0.25 D after 18 months of treatment.
 
The dropout rate evaluation one month after the inclusion of the last participant showed a dropout rate of 20%. Consequently, after clinical and statistical considerations, we increased the

		
total number of participants from 84 to 90, which corresponds to a 40% dropout rate. This was to ensure the sufficient power of the study.
 
Sample size: 90 children Non inferiority margin: Minimal clinically important difference: 0.13 mm (= 0.25D), SD 0.18

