3.4	
Hypotheses framework Describe hypotheses framework i.e. superiority, equivalence or noninferiority hypothesis testing and which group comparisons will be analysed
	
Noninferiority hypothesis:
 
H_0: DIMS is inferior to OKL, i.e. the difference in axial length change (DIMS – OKL) is > 0.13 mm.
 
H_1: DIMS is non-inferior to OKL, i.e. the difference in axial length change (DIMS – OKL) is ≤ 0.13 mm.
 
That is, we test whether the DIMS spectacle lens (new treatment) is not worse than the OKL (reference treatment) by more than 0.13 mm after 18 months.
 
The non-inferiority test is only applied to the primary outcome. All other outcomes are tested using standard superiority hypotheses.

3.5	
Statistical interim analyses and stopping guidelines (if applicable) Describe how and when interim analyses will be performed, and potential planned adjustment of significance level due to interim analyses. Describe guidelines for stopping the trial early.
	
No stopping guidelines. No planned interim analyses.

3.6	
Timing of outcome assessments and follow-up Describe time points at which outcomes/covariates will be measured (consider a figure to visualize the time windows of measurements – see appendix)
	
Primary and key secondary outcome: The primary outcome (axial length) and the key secondary outcome (overall eye length) is measured at baseline and every 6 months for 18 months on both eyes. If T0 (handout) exceeded 5 weeks from the baseline visit, a new measurement is conducted to replace the baseline measurement.
 
An additional visit was conducted at 1 month for both groups and additional visits for lens fitting and ocular health evaluation were conducted in the OKL group.
 
Covariates:
 
 - Age at baseline - Cycloplegic spherical equivalent refractive error at baseline - Axial length at baseline - Number of myopic parents (spherical equivalent refractive error ≤ -0.50D) at baseline 
Time-varying post-randomisation variables:
 
 - Adherence: Non-wear (patient-reported as the participants total amount of days without OKL or hours without DIMS). Non-wear since last visit is recorded at every visit during the study.

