5.1	Eligibility Summarize in- and exclusion criteria	
Inclusion criteria:
 
 - Myopic children aged 6 to 12 years: Myopia of the 6 to 8-year-olds (inclusive): -1.00 to -4.75 D spherical component and up to -2.50 D of regular astigmatism (both eyes). Myopia of the 9 to 12-year-olds (inclusive): -2.00 to -4.75 D spherical component and up to -2.50 D of regular astigmatism (both eyes). - Anisometropia \leq 1.50 D cycloplegic spherical equivalent refractive error. - Best corrected visual acuity at age 6 to 12 years (inclusive): 0.8 Snellen (equivalent to \geq 3/5 letter on the 0.8 line = 78 ETDRS letters) 
Exclusion criteria:

	
 - Manifest or intermittent squint. - Contraindications to the use of OKL comprising (not exhaustive): keratoconus, chronic allergic conjunctivitis and keratoconjunctivitis sicca. - Previous eye surgery. - Chronic eye disease demanding daily use of eye drops. - Non-compliance to eye examinations (unstable fixation or anxiety towards contact lenses). - Previous myopia control treatment. 
After trial commencement, project staff confused criteria of best corrected visual acuity in the 9 to-12 years group with the criteria of the 6 to 8-years group resulting in four children of 9 years old included using the 6 to 8-years old criteria for best corrected visual acuity. No children were excluded by this mistake. Preliminary referral or screening was not based on the visual acuity criteria. The visual acuity criterium was chosen to screen for abnormal vision. After clinical considerations, the visual acuity inclusion criteria in the 9–12-year group was too strict, as some of the younger children may not have fully matured visual development as 9-year-olds. Hence the inclusion criteria was adjusted to age 6 to 12 years (inclusive): 0.8 Snellen (equivalent to $\geq 3/5$ letter on the 0.8 line = 78 ETDRS letters), which reflects the visual acuity criteria used in the CONTROL-study (Jakobsen & Møller 2021)

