6.1	
Exposure and outcome definitions
 
Describe details on exposure i.e. assessment, definitions, units and thresholds or the intervention/treatment under study.
 
List and describe details on primary and secondary outcomes i.e. definition of outcome and timing, specific clinical measurements and units (i.e. mmol/mol) or any calculation or transformation of data to derive the outcome (i.e. sum score, change from baseline,
	
Primary Outcome Measure:
 
Axial length growth of the eye. Length is measured in mm [Time frame: 18 months of therapy]
 
Orthokeratology lenses induce flattening of the cornea, which reduces Axial length (AL). AL in the OKL group is adjusted for the decrease in central corneal thickness (CCT): adjusted $\text{AL}_{\text{follow-up}} = \text{AL}_{\text{follow-up}} + (\text{CCT}_{\text{BL}} - \text{CCT}_{\text{follow-up}})$.
 
The IOLMaster 700 version 1.90 (Carl Zeiss Meditech AG, Jena, Germany) measure the axial length, and is highly repeatable in healthy and myopic children (Garcia Arroyo et al. 2023, Huang et al. 2020) with a smallest detectable change (test-retest repeatability) of myopic children of 0.025 mm for spectacle users and 0.041 mm for OKL users (Garcia Arroyo et al. 2023).
 
Key Secondary Outcome Measure:
 
Overall Eye length growth. Length is measured in mm [Time frame: 18 months of therapy]
 
Overall Eye length is defined as: AL + Subfoveal choroidal thickness (SFCT).

-----	---	---

	logarithm, quality-of-life scoring algorithm)	The choroidal thickness is corrected for ocular magnification using the axial length, mean corneal radius, and refractive error entered in an algorithm. Open label: Outcome assessment was not blinded from knowledge of which intervention a participant received.

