6.3	Additional analysis methods	In case of non-inferiority, superiority is tested in the same population at 0.05 without a statistical penalty because of the

	
Describe any planned sensitivity and subgroup analysis including how subgroups will be defined (see appendix).
	
closed testing principle. Superiority is declared if the upper 95%CI bound is below zero (Figure 3).
 
In case of inferiority, a subgroup analysis of participants in the DIMS group with axial elongation exceeding emmetropic progression rate will be conducted as a hypothesis generating post hoc analysis.
 
Adherence: Sensitivity analysis of binary adherence “No-wear”, is repeated in groups of “high adherence”, “moderate adherence” and “low adherence” (see 4.2).
 
Protocol deviations: -Sensitivity analysis with and without the four children mistakenly included by technical error in the autorefractor apparatus result reading at baseline (see 4.2). Analysis is either provided in supplementary or by request.
 
-Sensitivity analysis of dropouts.
 
Additionally, post hoc analysis: - axial elongation after 18 months in relation to age at enrolment. - axial elongation after 18 months in relation cycloplegic spherical equivalent refractive error at baseline.

6.4	
Missing data Describe how missing data will be explored and which assumptions and methods will be used to handle missing data (i.e. multiple imputation)
	Missing data assumed to be missing at random (MAR) and will be handled by the mixed effects regression model.

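### The fallback analysis after inferiority selects DIMS children by their own outcome, in one arm, against an undefined rate, and its trigger has no decision rule

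*SAP*

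**What the plan says.** Section 6.3 plans for two results of the primary comparison. After non-inferiority, superiority is tested. Otherwise: "In case of inferiority, a subgroup analysis of participants in the DIMS group with axial elongation exceeding emmetropic progression rate will be conducted", described "as a hypothesis generating post hoc analysis". The SAP gives no figure, age or sex scale, time window or source for the emmetropic rate. It does not say what will be estimated in the subgroup, and it plans no corresponding OKL subgroup.

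The selection variable is also the primary outcome, which section 6.1 defines as "Axial length growth of the eye" over 18 months. The trial enrols "Myopic children aged 6 to 12 years" (section 5.1). Section 6.3 separately lists "axial elongation after 18 months in relation to age at enrolment" and the same analysis against baseline refraction, both post hoc.

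On the trigger, section 3.4 words the null hypothesis as "DIMS is inferior to OKL", meaning a DIMS minus OKL difference above 0.13 mm. Sections 4.1 and 6.2 say only when non-inferiority is concluded: the upper 95% limit must be at or below 0.13 mm and, in section 6.2, in both the ITT and PP analyses. No section's text says when inferiority is concluded.

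**The concern.** There are two linked problems.

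**The subgroup.** A group chosen because its members grew fast will show fast growth, whatever the treatment did. Any baseline factor that distinguishes these children may simply be a factor that makes myopic children grow faster. With no OKL children under the same rule, nothing shows whether DIMS does less for them. Because the cut-off is open, it would be settled after a disappointing result is known. Section 6.3's own template prompt asks how subgroups will be defined, so this definition belongs in the SAP.

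**The trigger.** If the upper limit exceeds 0.13 mm, the text offers only the word inferiority. Most such intervals would be compatible both with a difference inside the margin and with one beyond it. At stake are what starts the fallback analysis and how a missed primary objective is described.

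**Working it through.** **Inputs from section 3.3:** margin 0.13 mm, SD 0.18 mm, "given a significance level of 0.025 (one-sided test) and a power of 80" per cent, 32 evaluable children per group, final total 90, hence 90/2 = 45 per arm with no dropout.

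**Reproducing the SAP's figure.** Normal approximation: n = 2 × [0.18 × (1.960 + 0.842)/0.13]² = 30.1, so 31 per group. With the noncentral t distribution, power is 79.9% at 31 and 81.2% at 32. The stated 32 is reproduced.

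**1. Selection on the outcome.** Take growth in the DIMS arm as normal with SD 0.18 mm, and let d be the arm mean minus the cut-off. The SAP gives no value for d, so a range is assumed. Share selected = Φ(d/0.18). Selected mean minus arm mean = 0.18 × φ(d/0.18)/Φ(d/0.18).

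| d (mm) | Share selected | Of 45 | Selected mean minus arm mean (mm) |
|---|---|---|---|
| −0.2 | 13% | 6 | 0.29 |
| −0.1 | 29% | 13 | 0.21 |
| 0 | 50% | 22.5 | 0.14 |
| 0.1 | 71% | 32 | 0.09 |
| 0.2 | 87% | 39 | 0.05 |

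The excess arises with no variation in treatment effect at all. Over this range, membership runs from 6 to 39 children, depending on where the unstated rate lies relative to the arm mean.

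**2. What one arm can identify.** Suppose a baseline factor X changes prognosis by b per unit, the DIMS effect by t(DIMS) and the OKL effect by t(OKL). DIMS children alone show only the sum b + t(DIMS). With both arms, the difference in slopes is (b + t(DIMS)) − (b + t(OKL)) = t(DIMS) − t(OKL), and prognosis cancels. The one-arm subgroup cannot make that subtraction.

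**3. Age as an example.** Assume 18-month growth falls by 0.00 to 0.06 mm per year of age (not in the SAP), with age uniform over the enrolled range, total SD 0.18 mm and the cut-off at mean growth. One flat cut-off selects 50% to 80% of children under 9 and 50% to 28% of those 9 and over. A cut-off that follows the same age slope selects 50% of both groups at every slope. The age imbalance therefore depends on a flat rate, which the SAP neither adopts nor excludes. An age-specific rate would still leave other prognostic factors, such as parental myopia, mixed in.

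**4. The trigger.** SE = 0.18 × √(2/n), which is 0.0450 mm at n = 32 and 0.0379 mm at n = 45. The chance of missing non-inferiority at true difference δ is the noncentral t probability, with 2n − 2 degrees of freedom and noncentrality (0.13 − δ)/SE, of falling below the 97.5% t quantile. The chance of a lower limit above 0.13 mm is the upper-tail counterpart, with noncentrality (δ − 0.13)/SE.

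| n per arm | δ (mm) | Non-inferiority missed | Lower limit above 0.13 mm |
|---|---|---|---|
| 32 | 0 | 19% | about 1 in a million |
| 32 | 0.05 | 58% | about 1 in 10,000 |
| 45 | 0 | 8% | below 1 in a million |
| 45 | 0.05 | 45% | about 3 in 100,000 |

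These rates are for a single analysis. Requiring both ITT and PP to succeed can only raise the miss rates.

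**The case against.** The strongest defence is the SAP's own label: the analysis is hypothesis-generating, post hoc and conditional on one result, and it leaves the primary estimate, the margin and the non-inferiority rule untouched. That stands and limits the weight of the point. It does not rescue the design, because a hypothesis that DIMS works less well in certain children needs a comparison this subgroup lacks.

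A reader might infer that the analysis will present ordinary age-related growth as DIMS failure. The document does not support that. It never speaks of failure and names no test within the subgroup. A threshold at emmetropic growth also suggests an intention to set normal growth aside. The age imbalance needs both an assumed age slope and a flat cut-off. A simulation of 36 children with assumed slopes of 0.03 to 0.05 mm per year finds age significant in 33% to 80% of trials under a flat cut-off, but in about 5% under a matching age-specific one. Nor is the 33% to 80% a false-positive rate: age truly affects growth in that simulation, so it is power to detect a real prognostic association.

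A reader might also infer that a missed non-inferiority test will be reported as proof of inferiority. The SAP does not say so, and wording the null hypothesis as inferior is conventional. Figure 3 is described as showing possible scenarios adapted from a reporting guideline but is not visible here, so it may distinguish further outcomes. What stands is that the text gives no rule.

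Finally, 32 per arm is the pessimistic case. With 90 randomised and the 20% dropout recorded in section 3.3, 90 × 0.8/2 = 36 per arm remain, and the miss rate at a true difference of 0 is 14%. The elongation analyses by age and baseline refraction are not restricted to DIMS, so they cover part of the need, but no arm interaction is stated.

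**Conclusion.** The concern holds as a minor point. The subgroup is defined by a post-randomisation outcome, in one arm, against an undefined rate, and it cannot separate prognosis from treatment response. That conclusion follows from the design and needs no assumed growth figures; the excess of 0.05 to 0.29 mm rests on normality, the SAP's SD and an assumed range for the cut-off.

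The trigger lacks a decision rule in the text. For true differences of 0 to 0.05 mm, non-inferiority is missed in 19% to 58% of trials with 32 per arm and 8% to 45% with 45. Nearly all of those misses are inconclusive with respect to the margin. These figures assume a two-sample t comparison with SD 0.18 mm; the planned mixed model could be somewhat more or less precise.

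**What to change.** - **Replace the subgroup.** Fit exploratory arm-by-factor terms at 18 months for age, baseline refraction and number of myopic parents, in all randomised children. These covariates are already listed in section 6.2. Because OKL is an active comparator, the terms show where DIMS falls behind OKL, not the absolute DIMS effect.
- **If an emmetropic summary is kept,** fix an age-specific reference, its time window and its source before analysis, and report the share of children above it in both arms, descriptively.
- **State three verdicts** in sections 3.4 and 6.3: non-inferior if the upper limit is at or below 0.13 mm in both ITT and PP; worse by more than the margin if the lower limit is above 0.13 mm; otherwise non-inferiority not shown, inconclusive with respect to the margin. Say which verdicts start the exploratory analysis.

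The cost is a change of SAP wording and an additional model on data already collected. Interaction terms will have low power at this sample size, which is acceptable for a hypothesis-generating analysis provided estimates and intervals are reported.

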2.2	Describe briefly objectives and/or hypotheses	
In this non-inferiority randomised clinical trial, our primary goal is to compare the myopia control treatment efficacy of the new Defocus Incorporated Multiple Segments (DIMS) spectacle lenses to Orthokeratology lenses (OKL) after 18 months of therapy in myopic children. Secondly, we investigate the effect of choroidal thickness and pupil size on the treatment efficacy, as well as the difference in vision-related quality of life in the two groups prior to and after treatment initiation.
 
Primary outcome
 
 1. Axial length growth after 18 months of therapy. 
Key secondary outcome (“secondary” in clinicaltrial.org)
 
 1. Overall eye length growth after 18 months of therapy. 
Secondary outcome (“other” in clinicaltrial.org)
 
 1. To examine the effect of short-term changes in choroidal thickness on the treatment efficacy 2. To examine the influence of treatment on Pupil size after 6 months of therapy with OKL or DIMS spectacle lenses. 3. To examine the effect of pupil size on the treatment efficacy. 4. To evaluate the vision related quality of life using the questionnaire PREP2 prior to and 9 months after treatment initiation of OKL and DIMS spectacle lenses. 
Axial length is defined as a primary outcome in myopia progression clinical trials, and recommended to be reported as an absolute value (Sankaridurg et al. 2023).

Section 3: Study methods

3.1	
Study design Describe type of study (i.e. experimental/observational, parallel group/cross over, singlecenter/multicenter ect.) and describe briefly interventions
	
Single-centre non-inferiority randomized clinical trial. The participants are included at baseline before randomization.
 
Interventional study type with parallel groups. Active Comparator (reference treatment): OKL Experimental (new treatment): DIMS spectacle lens
 
The DIMS spectacle lenses comprise a central optical zone for correction of distance vision surrounded by a myopic defocus

-----	---	---

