		
zone with a relative power of +3.50 dioptres (D) comprised of about 400 defocus segments.
 
The OKL are custom-fit, form-stable, four-zone reverse geometry contact lenses with a 6 mm back optic zone diameter and 0.75 D compression factor. The lenses are used during sleep and temporary flatten the central cornea reducing central corneal power and steepening the paracentral cornea with relatively more corneal power.

3.2	
Randomization details (if applicable) Describe randomization i.e. allocation ratio, potential factors randomization will be stratified for and describe how and when randomization will be performed
	
Allocation ratio: 1:1 Number of possible assignments in the allocation table: 104 Block sizes: 4, 6 and 8.
 
The allocation sequence was generated by the data manager at OPEN, Open Patient Data Explorative Network, and concealed from research staff and participants using REDCap electronic data capture tools, a secure, web-based platform designed to support data capture for research studies.
 
No stratification.
 
Randomization is performed after inclusion at the end of the baseline visit by research staff using REDCap.
 
Open label: No blinding of participants or personnel from knowledge of which intervention a participant received.

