6.5	
Harms (only applicable in experimental studies) Describe the collection of safety data i.e. data on severity, expectedness, causality. Describe grouping and analyses planned i.e. incidence analyses on grade 3-4 events only.
	
The DIMS spectacle lens treatment is considered safe, with no treatment-related adverse events reported in a randomized controlled trial (Lam et al. 2020).
 
Regarding the OKL treatment, safety data was collected using the Efron score (Efron Grading Scale for Contact Lens Complications) for both eyes.
 
Adverse event was defined as; Any vision threatening or treatment-requiring conditions related to contact lens usage AND corneal staining Efron score Grade 2 or more.
 
Reporting zero events if no harms were observed.
 
Efron score is used in both treatment groups. The Efron score of the OKL group is compared to the DIMS group using a mixed model.

6.6	
Statistical software Specify statistical packages to be used for the analyses
	Stata

Jakobsen T, Gehr N & Møller F (2020): Correlation between change in cycloplegic spherical equivalent refractive error and change in axial length in Danish children aged 6 to 12 year. *Acta Ophthalmol*.

Jakobsen TM & Møller F (2021): Control of myopia using orthokeratology lenses in Scandinavian children aged 6 to 12 years. Eighteen-month data from the Danish Randomized Study: Clinical study Of Near-sightedness; TRreatment with Orthokeratology Lenses (CONTROL study). *Acta Ophthalmol (Copenh)* *aos.14911*.

[figure not shown]

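### The adverse event definition in SAP section 6.5 joins its two elements with AND and ties one of them to contact lenses, so the harm count depends on the reading and leaves out non-staining harms in DIMS children

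*SAP*

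**What the plan says.** Section 6.5 (Harms) contains the only adverse event definition in the SAP: "Any vision threatening or treatment-requiring conditions related to contact lens usage AND corneal staining Efron score Grade 2 or more". On reporting, it adds "Reporting zero events if no harms were observed".

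The section treats the two arms differently. For the spectacles it relies on an earlier trial: "The DIMS spectacle lens treatment is considered safe, with no treatment-related adverse events reported in a randomized controlled trial". For the contact lenses it states "Regarding the OKL treatment, safety data was collected using the Efron score", covering both eyes. It then adds "Efron score is used in both treatment groups" and plans one between-arm safety comparison: "The Efron score of the OKL group is compared to the DIMS group using a mixed model". Section 5.4 repeats that the Efron score goes into a mixed model. It does not mention adverse events, and none of the appendix table templates has an adverse event row.

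Section 3.1 identifies the devices. The new treatment is a spectacle lens ("Experimental (new treatment): DIMS spectacle lens"). The reference treatment consists of "four-zone reverse geometry contact lenses with a 6 mm back optic zone diameter", worn during sleep.

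**The concern.** There are two separate problems.

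The first is the connective. A capitalised AND between two clinical elements normally means that both must be present. On that reading the definition leaves out lens-related conditions that threaten sight or need treatment whenever staining is below grade 2, and a reader of the safety results would most want to see those. It may instead have been meant as a list of two things that each count. The SAP does not say which, so two analysts following it could report different counts from the same records. The trial is open label and outcome assessment is not blinded (sections 3.2 and 6.1), so that choice should not be left until the data are in view.

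The second is the phrase tying the first element to contact lens use. Children in the DIMS arm are given spectacles. The rule that counts serious conditions in the OKL arm cannot count them in a child who wears only spectacles.

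Section 2.1 presents DIMS as an alternative for children for whom OKL is not feasible or not wanted. Harms by arm therefore bear on how a non-inferiority result would be used, and a count that differs between arms partly by construction would mislead.

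**Working it through.** The SAP gives no event figure to reproduce, so the check applies the definition, under each reading, to each kind of record.

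Inputs: the definition, the Efron collection statements and the reporting rule (section 6.5); the devices (section 3.1); the recording of treatments used after dropout (section 4.2); the intention-to-treat rule (section 4.3).

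Below, *condition* means one that threatens sight or needs treatment, and *staining* means corneal staining of Efron grade 2 or more.

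| Record | Both required | Either counts |
|---|---|---|
| OKL: lens-related condition, with staining | counted | counted |
| OKL: lens-related condition, no staining | not counted | counted |
| OKL: staining, no such condition | not counted | counted |
| OKL: condition unrelated to lenses, no staining | not counted | not counted |
| DIMS, spectacles only: staining, with or without a condition | not counted | counted |
| DIMS, spectacles only: condition, no staining | not counted | not counted |
| DIMS-allocated, later wore contact lenses: lens-related condition, with staining | counted | counted |

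**Effect of the reading.** Let A be the number of records with a lens-related condition, B the number with staining and C the number with both.

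- Both required: count = C.
- Either counts: count = A + B − C.
- Difference = (A + B − C) − C = A + B − 2C = (A − C) + (B − C).

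Neither bracket can be negative, so the list reading never gives the smaller count. The readings agree only if A = B = C, that is, if the two elements always occur together. The SAP gives none of A, B or C, so the difference has a known direction and an unknown size.

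**Effect on the arms.** For a DIMS child who wears only spectacles, A = 0 by definition, and hence C = 0. If both elements are required, that child contributes zero whatever happens. If either counts, the child can contribute only through staining, B. The row for a DIMS condition without staining is not counted in either column, so settling the connective does not repair it.

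**Effect on the planned comparison.** The mixed model uses the Efron score itself, collected in both arms, and does not use the adverse event definition. It is unchanged under either reading. It compares grades on a contact lens complication scale and does not count events, so it does not replace the missing counts.

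**The case against.** The strongest opposing case is that the sentence is loosely worded but harmless. It can be read as a list, and then OKL conditions without staining do count, as does grade 2 staining in a DIMS child. The only planned between-arm safety comparison does not use the definition. The definition also follows directly on the statement about OKL safety data, so it may have been meant for the contact lens arm alone, with general adverse event collection left to a protocol that is not shown.

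Much of this stands, and it limits what can be claimed. A reader might infer more in four places:

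- *That DIMS children cannot have an event at all.* This is too strong. Under the list reading they qualify through staining. Under the joint reading a DIMS-allocated child who later wore contact lenses could qualify: section 4.2 records which treatments were used after dropout, and section 4.3 keeps such a child in the allocated arm. Only the spectacle-only child under the joint reading is wholly excluded.
- *That the safety comparison cannot be interpreted.* The SAP does not support this. Its stated comparison is of Efron scores and is untouched.
- *That a DIMS rate near zero will be reported.* With 90 children allocated 1:1, one could take about 45 per arm and compute an exact one-sided 95% upper limit for 0/45 of 1 − 0.05^(1/45) = 6.4%. The SAP plans no such rate or interval, and exactly 45 per arm is an assumption.
- *That the zero rule will turn uncounted events into a reported zero.* The rule refers to harms observed, not to whether the definition was met. A zero produced by the definition is a risk, because no other harm definition is given, but the text does not prescribe it.

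The objection does not remove the core. The SAP does not state the list reading, and that reading still leaves non-staining harms in spectacle-only children uncounted. If the definition was meant for the OKL arm alone, section 6.5 should say so, and no DIMS event count should then be given. The point does not depend on the unseen protocol, because the SAP states this counting rule itself.

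**Conclusion.** The point holds in a limited form. Section 6.5 states a counting rule that, taken literally, omits serious lens-related conditions without grade 2 staining and also omits grade 2 staining on its own. It admits a second reading with a different count, and under both readings it misses non-staining ocular harms in DIMS children who wear only spectacles. A low or zero DIMS count would be partly a product of the definition.

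The size cannot be stated. It depends on how often the two elements occur apart and on how many such conditions arose in the DIMS arm, and the SAP gives neither. The direction is known: the joint reading never counts more than the list reading, and the wording about contact lenses can only lower the DIMS count.

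The conclusion assumes that section 6.5 is the rule analysts will follow for event counts. It concerns event counts only. The Efron score comparison and the non-inferiority analysis are not affected. This is a correction that should be made to the safety reporting and does not threaten the trial's main conclusion.

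**What to change.** In section 6.5, replace the joint definition with two categories counted separately:

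- (a) ocular conditions that threaten sight or require treatment;
- (b) corneal staining of Efron grade 2 or more, keeping the grade the SAP already uses.

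Report the number of children with each category by arm, and show relation to the device in its own column instead of making it a condition for being counted. Counting the categories separately also settles the AND question.

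For (b), Efron data exist in both arms. For (a) in the DIMS arm, use whatever records are available. Section 6.5 documents only Efron collection, so such conditions may not have been recorded there. In that case state that no DIMS count is available, and do not report zero. Tie the zero-event sentence to this: zero may be reported only for a category and arm in which events were actually recorded.

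The cost is a change of SAP wording, a little recounting of records already held, and possibly a higher reported event count. The primary analysis and the Efron mixed model stay as they are.
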